10.6 Analyses of Secondary Endpoint

Echocardiographic parameters and their change from baseline will be summarized by randomized treatment group and scheduled assessment.

Mean differences between treatment groups in SET change from baseline at week 16 will be estimated via repeated-measures model including all observed values, with difference estimates and their 95% confidence intervals presented. The model will include IVRS stratification factor, baseline, treatment group, visit and the interaction of treatment group and visit. Individual subgroup analyses by the IVRS stratification factor and selected baseline covariates as listed in [Section 4.2](#) will be provided. Baseline covariates may also be included in the model one at a time in their original form.

10.7 Analyses of Exploratory Endpoints

Both continuous and categorical exploratory endpoints will be summarized descriptively by cohort, treatment group, and scheduled assessment.

Mean differences between treatment groups in SV, LVESD, LVEDD, and HR change from baseline at scheduled assessments will be estimated via repeated-measures model

including all observed values, with difference estimates and their 95% confidence intervals presented. The model will include IVRS stratification factor, baseline value, treatment group, visit and the interaction of treatment group and visit.

NT-proBNP will be summarized descriptively and analyzed in the same principle as echocardiographic parameters.

For clinical outcome endpoints specified in [Section 4.1.4](#), subject incidence rates for each treatment group will be provided.

For each subject, the first dose date of IP will be used as the starting point for all time-to-event calculation. For each qualifying event, the onset date adjudicated by CEC will be used as event onset date for time-to-event calculation. If not otherwise specified, the adjudicated events that occurred between the first dose date of IP and the end of study date will be included in the analyses of the time-to-event clinical outcome endpoints. Subjects who did not experience a qualifying event will be right censored at the end of study.

Supraventricular tachycardia and ventricular tachycardia arrhythmias will be identified from the corresponding eCRF forms. Subject incidence of supraventricular tachycardia and ventricular tachycardia arrhythmias requiring treatment from initiation of IP to end of study will be summarized for each treatment group.

10.8 Safety Analyses

Adverse events that occur after a subject's EOS date will be excluded.

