2.2.2.1 Studies in Healthy Volunteers

CY 1111, a first-in-human clinical study with omecamtiv mecarbil, was a randomized, double-blind, placebo-controlled, 4-period crossover, dose escalation study designed to evaluate the safety, tolerability, and PK/PD profile of omecamtiv mecarbil administered IV to healthy male volunteers ([Teerlink et al, 2011](#)). This study included a total of 33 subjects who received infusions of omecamtiv mecarbil at doses ranging from 0.005 mg/kg/hr to 1.0 mg/kg/hr for up to 6 hours. The exposures of omecamtiv mecarbil, as measured by area under the curve (AUC) and maximum observed concentration (C_{max}), were approximately dose proportional, with an AUC of 159 (57 standard deviation) ng•hr/mL for treatment administered at an infusion rate of 0.005 mg/hr/kg and 30400 ng•hr/mL when administered at a rate of 1 mg/hr/kg; corresponding C_{max} values for those administration rates were 8.70 (2.20) ng/mL and 1340 ng/mL. The mean clearance ranged from 125 to 207 mL/hr/kg and the mean half life ranged from 17.1 to 23.2 hours and increased slightly with increasing doses. The mean steady state distribution volume was dose independent and ranged from 3.6 to 5.2 L/kg. At the dose of 0.5 mg/kg/hr over 6 hours, the mean (standard deviation [SD]) C_{max} was 905 (183) ng/mL. Across the dosing levels evaluated in CY 1111, omecamtiv mecarbil infusions demonstrated generally linear PK with dose-proportional increases in C_{max} . Concentration-dependent PD effects on cardiac function as measured by echocardiography were observed. These PD effects included statistically significant placebo corrected increases from baseline in SET, Doppler-derived stroke volume, left ventricular ejection fraction (LVEF), and fractional shortening.

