50 mg BID at the week 4 visit based on steady state concentration prior to investigational product (IP) administration ($C_{predose}$) result from week 2. Subjects who do not have a week 2 PK value in time for dose adjustment at the week 4 visit will be up-titrated at week 8 based on the steady state $C_{predose}$ result from week 2, if available. Subjects will be up-titrated at the week 4 or week 8 visits only if the week 2 $C_{predose}$ is < 200 ng/mL. Subjects with a week 2 $C_{predose} \geq 200$ ng/mL (or not available at week 8) will continue at 25 mg BID for the remaining of the study. Subjects randomized to placebo or to 25 mg BID will receive the assigned IP throughout the study. IP compliance will also be monitored. PK analysis and dose assignment will be blinded to the study team. To maintain blinding, all subjects will receive new IP supply at the week 4 and week 8 visits. The study includes transthoracic echocardiographic assessments (screening, week 8, and week 16). Enrollment of subjects with atrial fibrillation/flutter at the time of screening will be limited to approximately 20% of planned enrollment. Randomization will be stratified by presence or absence of atrial fibrillation/flutter via the interactive voice response system/interactive Web response system (IVRS/IWRS). An independent DMC will perform regular formal unblinded review of the accumulating study data. An independent CEC will adjudicate deaths, all hospitalizations, and selected nonfatal cardiovascular (CV) events (including possible MI or ischemia). The end of study (EOS) visit will be performed 4 weeks after the last dose of IP (Week 20 +3 days).

Vital signs, physical examinations, ECGs, Adverse Event/Serious Adverse Event assessments, clinical laboratory evaluations (see [Table 3](#)), and collection of concomitant medications will be performed at screening and at specified times per the Schedule of Assessments ([Table 2](#)). The overall study design is described in a [study schema](#) at the end of the protocol synopsis section.

The study endpoints are defined in [Section 10.1.1](#).

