6.2.1.1 Dosage, Administration, and Schedule

Eligible outpatient subjects will be randomized and will initiate administration of IP (omeamtiv mecarbil or placebo). Day 1 is defined as the calendar day when treatment with IP is initiated. The first administration of IP should be on the day of randomization but not later than 5 calendar days after randomization. The time when ingestion of the first dose of IP is completed is defined as Time = 0 hours. Baseline procedures must be completed before initiation of IP and can be performed on the same day.

IP will be administered orally BID in the morning and evening by the subjects and can be taken under fasted or fed conditions. IP will be swallowed whole (not chewed) and taken with water as instructed in the IPIM. Administration of each morning and evening dose is to be taken at approximately the same time of day (12 ± 3 hours from the most recent previous dose). If IP cannot be taken or has not been taken within this window, the dose should be recorded as missed and the next dose should be taken at the regular time.

Administration of IP will start with the morning dose on day 1 and will end with the morning dose on the day of the subject's week 16 visit. The quantity, date and time, lot number, and bottle number of investigational product is to be recorded on each subject's eCRF.

6.2.1.2 Rules for Withholding Investigational Product due to Myocardial Ischemia or Infarction, Abnormal Blood Pressure or Heart Rate

Omecamtiv mecarbil may result in signs and symptoms of myocardial ischemia or infarction, as described in Section 7.1 of the Investigator's Brochure (eg, increases in HR, dizziness, dyspnea, hypotension, chest discomfort or pain, ST-segment depression on ECG, and/or elevations in troponin I or T). If a subject reports clinical signs or symptoms suggestive of myocardial ischemia or infarction, and/or experiences changes in BP or HR, withholding of IP should be considered. No antidote to omecamtiv mecarbil exists. Standard medical therapies should be used in the presence of signs or symptoms of myocardial ischemia.

The following are mandatory rules for withholding IP:

- The subject experiences clinical signs or symptoms, including ECG changes, consistent with myocardial ischemia or infarction as determined by the investigator
- The subject experiences a symptomatic decrease in systolic BP on 2 successive measurements

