^a If early discontinuation, week 20 (EOS) assessments should be performed as close as possible to time of discontinuation

^b Serious adverse events are collected from signing the informed consent until 30 days after the last dose of IP or EOS, whichever is later, adverse events and PEPs from randomization until EOS, recording of PEPs and hospitalization only during visits to the study site (day 1, weeks 2, 4, 8, 12, 16, 20 [EOS]); if subject is not seen at the study site, AEs/SAEs/PEPs can be collected by phone

^c Predose in the morning, at study site

^d Performed as close as possible after the collection of PK sample at 2 hours \pm 30 minutes following IP administration.

^e If cardiac troponin is measured locally to evaluate suspected myocardial ischemia or infarction, send samples for troponin I/CK-MB, and PK (up to 5 days after last dose of IP) to the central laboratory

^f Serum pregnancy testing in females of childbearing potential, FSH/LH or estradiol at screening only, and only if applicable per exclusion criteria.

^g IP is taken twice daily except on the last day of administration (week 16 visit). Subjects randomized to 37.5 mg BID target dose and 50 mg BID target dose will initiate administration at 25 mg BID. Subjects will be up-titrated to 37.5 mg BID or 50 mg BID target dose at the week 4 visit based on steady state $C_{predose}$ result from week 2. Subjects who do not have a week 2 PK value in time for dose adjustment at the week 4 visit, will be up-titrated at week 8 based on steady state $C_{predose}$ result from week 2, if available. Subjects will be up-titrated at the week 4 or week 8 visits only if the week 2 $C_{predose}$ is < 200 ng/mL. Otherwise, they will continue at 25 mg BID.

^h Details of IP dispensation and reconciliation are described in the IPIM; dispensation and reconciliation timepoints may differ from the timepoints shown above; IP not dispensed at week 16 visit.

ⁱ Paper Diary will be dispensed at Day 1 and will be collected at week 16. Subjects will be instructed to enter each administration of IP from Day 1 to week 16 or early termination. The date and time of administration will be noted.

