9.2.2 Reporting Procedures for Serious Adverse Events

The investigator is responsible for ensuring that all serious adverse events observed by the investigator or reported by the subject that occur after signing of the informed consent until 30 days after the last dose of IP or Safety Follow-up Visit/End of Study, whichever is later, are recorded in the subject's medical record and are submitted to Amgen. All serious adverse events must be submitted to Amgen within 24 hours following the investigator's knowledge of the event via the applicable eCRF.

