6.1 Study Time Points

Randomization Date

The randomization date for each subject is the date the investigator (or designee) confirms in the IVRS that the subject has met all eligibility criteria and is randomized.

Enrollment Date

The enrollment date is the same as the randomization date. The enrollment date is a derived field on the electronic case report form (eCRF) page.

First Dose Date of Investigational Product (IP)

For each subject, the First Dose Date of Investigational Product is defined as the date of the first administration of IP as recorded on the IP administration eCRF page.

Study Day 1

The date of the first investigational product (IP) administration or the date of enrollment for subjects who were not administrated any dose of IP.

Study Day

For each subject and a given date of interest, study day is defined as the number of days since study day 1:

Study day = (date of interest – study day 1 date) + 1.

If the date of interest is prior to the study day 1:

Study day = (date of interest – study day 1 date).

Last Dose Date of Investigational Product

For each subject, the Last Dose Date of Investigational Product is defined as the date of the last administration of investigational product.

End of Study (EOS) Date

For each subject, the end of study date is the date recorded on the End of Study eCRF.

Study End Date

The study end date is the last end of study date of all randomized subjects.

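### The SAP safety tables stop at each subject's EOS date, although the protocol collects serious adverse events to the later of EOS and 30 days after the last dose

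*SAP*

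**What the plan says.** SAP section 10.8 gives one rule for all safety analyses: "Adverse events that occur after a subject's EOS date will be excluded". Sections 6.4 and 10.8.1 end the treatment-emergent window at the same point. The date is subject-specific: "For each subject, the end of study date is the date recorded on the End of Study eCRF" (SAP 6.1). The Appendix B algorithm classifies onset only against the first dose and carries no end date.

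Protocol Table 2, footnote b, sets a longer window for serious events: "Serious adverse events are collected from signing the informed consent until 30 days after the last dose of IP or EOS, whichever is later". Protocol 9.2.2 has investigators record them and submit them to the sponsor through the eCRF "until 30 days after the last dose of IP or Safety Follow-up Visit/End of Study, whichever is later".

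On timing, dosing "will end with the morning dose on the day of the" week 16 visit (Protocol 6.2.1.1), and "The end of study (EOS) visit will be performed 4 weeks after the last dose of IP" (Protocol 3.1). Table 2 footnote a adds: "If early discontinuation, week 20 (EOS) assessments should be performed as close as possible to time of discontinuation".

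Two other protocol sections, 7.4 and 9.2.2.2, describe SAE reporting only as far as EOS.

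**The concern.** The later-of wording in the protocol provides for the 30-day limit to fall after EOS, and the SAP makes no use of that case. An SAE, including a fatal one, with onset between EOS and the 30-day limit should be in the trial data and would then be left out of the safety tables. An event that starts before EOS and later proves fatal is not clearly excluded, and this point does not cover it.

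No other analysis picks up the gap events. The outcome analyses in SAP 10.7 also stop at the end-of-study date. SAP section 11 declares only the dropped heart-failure-treatment covariate and the changed PK analysis set definition.

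Safety and tolerability is a primary objective, and the arms have about 20 subjects each. One omitted subject with an SAE changes an arm's incidence by 1/20 = 5 percentage points.

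**Working it through.** **Inputs**
- Last dose: morning of the week 16 visit, Day 112, window ±3 days (Protocol 6.2.1.1, Table 2).
- EOS: Day 140, window +3 days (Protocol 3.1, Table 2).
- SAE window: later of EOS and last dose + 30 days (Protocol 9.2.2, footnote b).
- SAP cut-off: EOS date (SAP 6.1, 10.8), assumed to be the week 20 visit date for completers.

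**The plan's own figures.** 112 + 28 = 140, which matches the schedule. Twice-daily dosing for 111 days plus one morning dose is 2 × 111 + 1 = 223 tablets, which matches the planned total in SAP 6.4 and confirms a last dose on Day 112.

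**Formula.** Gap in days = max(0, last dose day + 30 − EOS day).

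**On schedule.** 112 + 30 − 140 = 2, so Days 141 and 142 are collected and excluded.

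**EOS 28, 29, 30 or 31 days after the last dose (Protocol 3.1).** Gap 2, 1, 0 or 0 days.

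**All Table 2 windows.** Last dose on Days 109 to 115 and EOS on Days 140 to 143 give 28 date pairs. These are calendar combinations, not probabilities.

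| Gap (days) | 0 | 1 | 2 | 3 | 4 | 5 |
|---|---|---|---|---|---|---|
| Pairs | 14 | 4 | 4 | 3 | 2 | 1 |

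The 6 pairs with a gap of 3 to 5 days place EOS only 25 to 27 days after the last dose, which conflicts with Protocol 3.1. The 16 pairs with an interval of 28 to 31 days give gaps of 0, 1 and 2 days in 8, 4 and 4 pairs.

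**EOS brought forward (assumed lags from last dose to EOS).** Gap = 30 − lag:

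| Lag (days) | 0 | 7 | 14 | 21 | 28 | 30 |
|---|---|---|---|---|---|---|
| Gap (days) | 30 | 23 | 16 | 9 | 2 | 0 |

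This needs usable data after EOS. Protocol 8.3.2 gives four reasons for leaving the study. Death, loss to follow-up and consent withdrawal (limited by Protocol 8.1) leave little or none, so sponsor-decision removals are the main case.

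**IP stopped but subject stays in the study, EOS on Day 140.** Last dose on Day 110 or earlier gives 0 days, Day 111 gives 1 and Day 112 gives 2. Protocol 8.1 and 12.4 let data collection continue for these subjects. They have a longer gap only if footnote a is read as closing the study, which it does not say.

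**Drug exposure in the gap.** In the first-in-human study (IV, healthy volunteers) "the mean half life ranged from 17.1 to 23.2 hours" (Protocol 2.2.2.1). Over 28 days: 672 h / 23.2 h = 29.0 and 672 h / 17.1 h = 39.3 half-lives. For completers the gap therefore lies about 29 to 39 half-lives after the last dose. If EOS is brought forward to near the last dose, the excluded days include the early post-dose period.

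**The case against.** The strongest reply is that a collection window is not an analysis window. The protocol's adverse event analysis section (10.5.4.1) sets no end date of last dose + 30 days. Non-serious events, hospitalizations and adjudication all end at EOS or study completion, and the SAP follows that pattern. Protocol 7.4 and 9.2.2.2 even end SAE reporting there, so the SAP agrees with one of the protocol's two readings. No visit or call is scheduled after EOS, so later events would come to light only through unscheduled reports. They would still reach the sponsor within 24 hours and be followed up, so only the summary tables are affected. The completer gap is about 2 days, and the completion rule for the End of Study eCRF is not in the documents. A separate listing of post-EOS SAEs would show them without changing the treatment-emergent definition.

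Much of this stands as a limit on size. The gap is short for most subjects, the silence of SAP section 11 carries little weight, and the protocol needs its own correction. It does not remove the conflict. Section 9.2.2 and footnote b are the provisions that set the SAE window, and the SAP rule discards events that they require to be submitted. A listing would make those events visible but leave the incidence tables incomplete.

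**Conclusion.** The concern holds. As written, the SAP excludes SAEs that the protocol requires to be collected. The gap is 2 days for a completer on schedule, 0 to 2 days when Protocol 3.1 is followed, and at most 5 days across the Table 2 windows. If EOS is brought forward and later data may be used, it is 30 days minus the lag from last dose to EOS.

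The completer figures assume that the End of Study eCRF carries the week 20 visit date. If it carries a date at least 30 days after the last dose, the gap is 0.

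For completers the case rests on agreement with the protocol's own SAE window, not on expected drug effect. The documents give no basis for stating a number of affected subjects or events, or a difference between arms. The change should be made because it is cheap and concerns a primary objective.

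**What to change.** - In SAP 6.4, 10.8 and 10.8.1, include serious adverse events, fatal ones among them, with onset up to the later of the EOS date and last IP dose date + 30 days, subject to the consent-withdrawal limit in Protocol 8.1.
- Extend the treatment-emergent definition for serious events in the same way, so that the SAE and treatment-emergent tables agree. Keep EOS for non-serious events and footnote both cut-offs.
- Secondary edits: put the end dates in the Appendix B algorithm, and correct the reference in 10.8.1, which points to section 6.3 although the definition is in 6.4.
- State which date counts as EOS when a subject stops IP but stays in the study, and clarify footnote a accordingly.
- Reconcile Protocol 7.4 and 9.2.2.2 with 9.2.2 and footnote b.

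The cost is short SAP edits, one date condition in the programs and a protocol clarification. No new data are needed if SAEs are collected as section 9.2.2 requires. The downside is small: serious and non-serious events have different end dates, and the added days are covered only by unscheduled reporting.

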10.8.1 Adverse Events

The Medical Dictionary for Regulatory Activities (MedDRA), using the current version at the time of final database lock, will be used to code all adverse events (AEs) to a system organ class and a preferred term. All adverse event tables will be summarized by actual treatment group. Treatment-emergent adverse events are events with an onset after the administration of the first dose of investigational product through the end of study as defined in [Section 6.3](#).

The subject incidence of AEs will be summarized for all treatment-emergent AEs (TEAEs), serious AEs, AEs leading to withdrawal of investigational product, fatal AEs, and AEs of interest (EOI).

Subject incidence of all treatment-emergent AEs, serious AEs, AEs leading to withdrawal of investigational product, and fatal AEs will be tabulated by system organ class and preferred term in descending order of frequency.

Summaries of treatment-emergent and serious AEs by preferred term in any treatment arm will be provided in descending order of frequency.

Subject incidence of EOIs (structured MedDRA queries and/or customized queries) will be summarized according to the EOI search strategy categories.

10.8.2 Laboratory Test Results

Laboratory results and their change from baseline will be summarized by actual treatment group and scheduled assessment for a subset of laboratory analytes provided in the protocol, Table 3. These include creatinine, creatine kinase, total bilirubin, direct bilirubin, alkaline phosphatase, alanine aminotransferase, aspartate aminotransferase, NT-proBNP, troponin, CK-MB and digoxin.

Shift tables will be provided by treatment group, which will be based on modified CTCAE grades and will compare baseline laboratory values with the most extreme post-baseline values. Summaries of subjects with post-baseline laboratory values with a CTCAE grade ≥ 3 , if available, will be provided. The following shift tables will be generated:

- Total bilirubin (blood bilirubin increased)
- ALP (alkaline phosphatase increased)
- AST (SGOT) (aspartate aminotransferase increased)
- ALT (SGPT) (alanine aminotransferase increased)

Number and percentage of subjects of each troponin status “undetected” (< 0.016 ng/mL), “detected” ($0.016 – 0.04$ ng/mL), and “elevated” (> 0.04 ng/mL) at each scheduled assessment will be summarized overall and by baseline status. Change of troponin status from baseline to the worst post-baseline will be tabulated. These summaries will be repeated by using different thresholds of upper reference limit (URL) in defining status: URL, 2xURL, 3xURL, 4xURL, 5xURL, 10xURL.

Summaries will also be presented by treating troponin as continuous variable. Troponin values below or above the quantifiable limits will be treated as equal to the limits.

CK-MB using different thresholds of URL, will be summarized and presented in the similar way as for troponin.

